### 10.7.3 Pregnancy Testing

Results of serum and urine pregnancy tests are listed for the SAF.

### 10.7.4 Culture-based sterility Test on EDS-EP

The absolute count (n) and percentage (%) of potentially contaminated infusions at any time and potentially contaminated infusions by visit is summarized for the SAF. All sterility test data and process data are listed for the SAF.

### 10.7.5 Process Events

The absolute count (n) and percentage (%) of EDS process failures at any time and potentially contaminated infusions by visit is summarized for the SAF. All EDS process data is listed for the SAF as outlined in section 10.5.

### 10.7.6 Vital Signs

All Vital Sign data are included in a listing for the SAF.

Vital Sign results and change from baseline are summarized by summary statistics on scheduled visits for the SAF. The absolute counts (n) and percentages (%) of patients with clinically notable findings are included in a separate summary for the SAF. The absolute counts (n) and percentages (%) of patients with at least one clinically notable change from baseline and summary statistics of the most extreme clinically notable increase and decrease from baseline are presented in separate summaries for the SAF.

### 10.7.7 Physical and Neurological Examination

All physical and neurological examination data are included in separate listings for the SAF. Neurological examination data is listed by type in separate listings (Cranial Nerves, Motor, Sensory, Reflexes and Cerebellar and Other)

Investigator assessment of the examination of physical and neurological examination data are summarized as categorical data as described in section 8.1 by visit for the SAF.

### 10.7.8 ECGs

All ECG data are included in a listing for the SAF.

Absolute counts (n) and percentages (%) of investigator interpretation of ECG results are summarized for each scheduled visit for the SAF.

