Statistical Methods	Descriptive statistics (n, mean, standard deviation [SD], median, minimum, and maximum) will be provided for all continuous efficacy measures for actual values and changes from baseline of Study IEDAT-03-2018 at each time-point. For categorical variables, the number and percentage of patients in each category will be presented at each time-point. The analysis of long-term efficacy of EDS-EP is an exploratory objective of this extension study, and will be based on the results for the “Modified” International Cooperative Ataxia Rating Scale (mICARS), and the Clinical Global Impression of severity and change (CGI-S/C). The mean (SD) change from baseline at each time-point will be evaluated for the mICARS and the CGI-S. For the CGI-Change, the proportion [n(%)] of patients rated as improved, as well as those showing no change or worsening, at each time-point will be calculated. Additional analyses will be performed to determine the change in each of the efficacy measures compared to the baseline of the IEDAT-02-2015 study, comparing patients who were treated with EDS-EP throughout the double-blind and open-label treatment periods vs. those who received placebo for varying periods in Study IEDAT-02-2015, before being switched to the active treatment. As a secondary objective, similar descriptive analyses will be performed to evaluate the long-term effects of EDS-EP on health-related Quality of Life (QoL), as assessed by the EQ-5D-5L scale. Descriptive statistical analyses of changes from baseline will be performed for all safety parameters. Abnormal and clinically notable values will be identified and listed for each parameter, as appropriate.
Analysis Populations	The following analysis sets will be used:  1) Efficacy Population (EP) : All patients who enter study IEDAT-03, have a baseline efficacy assessment in study IEDAT-03, and who received at least one dose of study medication and had at least one post-baseline efficacy assessment of the primary efficacy variable in this extension study.  2) Safety Population (SP) : All subjects who receive a dose of study medication, and have at least one post-dose safety assessment will be included in the safety analyses.

**Schedule of Visits and Assessments: 1st year of open-label extension treatment (Visit 1 to Visit 13 to be replicated for the second year onwards)**

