### 3.4 Efficacy and Safety Variables

#### Primary Endpoint

*The primary objective is to monitor and evaluate the long-term safety and tolerability of EDS-EP in AT patients. This will be done based on the occurrence of Treatment-Emergent Adverse Events (TEAEs), including Serious AEs and discontinuations due to AEs, and changes in vital signs, laboratory parameters, ECGs and physical/neurological examination findings.*

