### **Physical and Neurological Examination**

*Physical examinations are performed as specified on the Schedule of Visits. Physical examination includes an examination of general appearance, skin, neck (including thyroid), eyes and ears, nose, mouth, throat, lungs, heart, abdomen, back, lymph nodes, extremities and nervous system. Abnormal results are identified by the investigator and specified as clinically significant or not clinically significant. All results are recorded on the ‘Physical Examination Pre-Infusion’ or ‘Physical Examination Post Infusion’ eCRF pages. Neurological Examination results are recorded on the ‘Neurological Examination’ eCRF page.*

Physical Examinations are performed post infusion at all visits with additional pre-infusion assessments at Month 6, Month 12 etc. Neurological Examinations are performed pre-infusion at Month 6, Month 12 etc.

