### **ECG variables**

Electrocardiogram (ECG) evaluations are performed every 6 months in accordance with the Schedule of Study Events. At each evaluation, three ECG assessments are performed in succession, approximately 10 minutes apart. The investigator’s interpretation of ECG results (‘normal’; ‘abnormal, clinically significant’; ‘abnormal, not clinically significant’) is recorded on the ‘ECG’ eCRF page.

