## 8. Analysis Methods

### 8.1 General Methods

For continuous variables, the mean, standard deviation (SD), minimum, median and maximum as well as 1st and 3rd quartile (Q1, Q3) are presented, together with the total number of observations and the number of non-missing values. Unless otherwise specified minimum and maximum values are reported to the same number of decimal places as the recorded measurements, mean, median, 1st and 3rd quartile are reported to one more decimal place and standard deviation one additional decimal place more than the mean.

For categorical variables, absolute and relative frequencies are reported. Relative frequencies are based on all observations and reported as a percentage to one decimal place. Unless otherwise specified percentages are based on the number of patients with data and are not calculated for missing categories.

Adverse events, medical histories and concomitant medications are reported on a patient basis, i.e. if a patient reported several events coded to the same coding term the patient is counted only once at the respective level of display. The percentages are calculated using the number of patients in the population Analysis Set as the denominator.

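### The primary safety endpoint names changes in ECG and examination findings, but the SAP's tables do not identify which abnormalities are new or worsened since baseline

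*SAP*

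**What the plan says.** SAP 3.4, repeating protocol 7.3, bases the primary safety evaluation on treatment-emergent adverse events and on "changes in vital signs, laboratory parameters, ECGs and physical/neurological examination findings". The statistical methods in the protocol synopsis add: "Descriptive statistical analyses of changes from baseline will be performed for all safety parameters".

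For the ECG, SAP 10.7.8 plans a listing and one summary: "Absolute counts (n) and percentages (%) of investigator interpretation of ECG results are summarized for each scheduled visit for the SAF". For the examinations, SAP 10.7.7 plans listings and this: "Investigator assessment of the examination of physical and neurological examination data are summarized as categorical data as described in section 8.1 by visit". SAP 8.1 offers only absolute and relative frequencies for categorical data. Index 12.1 has one summary table each for physical examination, neurological examination and ECG (Tables 14.3.3-3.1, 14.3.3-3.2 and 14.3.3-4). The only shift tables in the index are 14.3.2-3.1 (special laboratory parameters) and 14.3.3-6.2 (bone mineral density). SAP 3.6, which records changes from the protocol, does not mention the matter.

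**The concern.** The endpoint speaks of change, while the ECG and examination tables show status at each visit. A by-visit table says how many patients are abnormal now. It does not say how many were normal at baseline and became abnormal, or moved from not clinically significant to clinically significant. A steady percentage can reflect the same patients throughout or a turnover of different patients, and departures blur this further because "percentages are based on the number of patients with data".

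The unit counted also needs fixing. SAP 7.4.8 says that at each evaluation "three ECG assessments are performed in succession, approximately 10 minutes apart", and SAP 8.1 also states: "Relative frequencies are based on all observations". No rule reduces three ECGs to one result per patient. The physical examination raises a similar question. It is done after infusion at all visits, "with additional pre-infusion assessments at Month 6, Month 12 etc", so a 6-monthly visit yields two results.

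At stake is whether the study report can answer, without hand counting from listings, how many patients developed a new ECG or examination finding.

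**Working it through.** The documents give no figure to reproduce: the study is descriptive and has no formal sample size calculation. The check is a comparison of texts, followed by arithmetic on what by-visit counts can show.

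**1. What the SAP tabulates for each component**

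| Component | Change from baseline tabulated? | SAP |
|---|---|---|
| Vital signs | Yes: change, and patients with at least one notable change | 10.7.6 |
| Laboratory, continuous | Yes: change to each visit | 10.7.2 |
| Special laboratory, investigator interpretation | Yes: shift table, each visit against baseline | 10.7.2 |
| Bone mineral density | Yes: change in z-score, and shift table of interpretation | 10.7.10 |
| ECG interpretation | No: by-visit counts | 10.7.8 |
| Physical and neurological examination | No: by-visit counts | 10.7.7 |

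Of the components that the endpoint sentence names, only the ECG and the examinations have no tabulated change.

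**2. What by-visit counts can show**

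Suppose the same N patients are assessed twice, with a abnormal at baseline and b at a later visit. The number newly abnormal lies between max(0, b − a) and min(b, N − a). Take N = 150, the maximum in protocol 16.2.1, and assume equal rates at both times:

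- 5% (a = b = 8): 0 to 8 newly abnormal.
- 10% (a = b = 15): 0 to 15.
- 20% (a = b = 30): 0 to 30.

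The planned table is the same across each range. A shift table gives the number exactly.

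**3. With patients leaving**

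Assume 15/150 abnormal at baseline and 12/120 at Month 6. The table reads 10% and 10%. Between 0 and 12 of the 12 abnormal patients could have been abnormal at baseline, so between 0 and 12 are new.

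**4. Plausible values inside the range (illustration only)**

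Let a proportion q be abnormal at every visit, and let an abnormal result persist to the next visit with probability r. The percentage stays flat if the chance of a new abnormality per visit is p = q(1 − r)/(1 − q). The share newly abnormal at Month 6 or Month 12 is 1 − (1 − p)². Take 90 patients seen throughout.

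- q = 10%, 81 normal at baseline: r = 0.9 gives p = 1.11% and 2.2% (1.8 patients); r = 0.7 gives 3.33% and 6.6% (5.3); r = 0.5 gives 5.56% and 10.8% (8.7).
- q = 20%, 72 normal at baseline: r = 0.9 gives p = 2.5% and 4.9% (3.6 patients); r = 0.7 gives 7.5% and 14.4% (10.4); r = 0.5 gives 12.5% and 23.4% (16.9).

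If half of these are reported as adverse events, 0.9 to 4.4 of 81, or 1.8 to 8.4 of 72, would be identifiable as new only from listings. Prevalence, persistence, attrition and the reporting share are all assumptions.

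**5. Why a worst-value count should not be the main table**

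In the same model at q = 10%, over ten 6-monthly ECGs, 1 − (1 − p)¹⁰ is 11% for r = 0.9 and 44% for r = 0.5, although prevalence never changes. Follow-up this long is foreseen: the adverse event intervals in SAP 7.1 run to day 1824 and continue.

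**The case against.** The strongest answer is that little is lost. Protocol 14.1.1 makes new instrumental abnormalities adverse events and sets no threshold of clinical significance. Read literally, every new abnormal ECG should reach the adverse event tables. Clinically significant ECGs are repeated until normal (protocol 13.3), and all results are listed by patient. This stands and makes the gap small. What remains is under-reporting and, if investigators apply a significance filter in practice, findings that they rated not clinically significant.

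Second, protocol 16.2.5 asks only that these items be listed and summarized, which the SAP does. A reader might infer that the SAP breaches the protocol. The documents do not settle that: the synopsis sentence and the endpoint wording ask for more than 16.2.5 does. It is safer to say that the texts do not match and that SAP 3.6 is silent.

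Third, a reader might infer that newly abnormal patients appear nowhere but in listings. They do not vanish: they enter the by-visit counts as abnormal. Only their identification as new or worsened is missing.

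Fourth, whether the eCRF holds one ECG rating per evaluation or three cannot be seen from the documents, nor whether the final ATTeST ECG was in triplicate. The unit is therefore something to state, not a demonstrated error. Taking the worst of three tracings against a single baseline tracing could create false shifts.

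Fifth, one worst category across all body systems would probably be saturated at entry. The examination covers skin, eyes and nervous system (protocol 13.1), and protocol 7.3 describes a progressive neurologic disease with cutaneous and ocular telangiectasia in 90%. This stands, and is why the physical examination shift should be by body system.

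**Conclusion.** The point holds as a minor reporting gap. The primary safety endpoint and the synopsis name change, but SAP 10.7.7, 10.7.8 and index 12.1 give only by-visit frequencies for ECG and examinations. The SAP already tabulates change for vital signs, laboratory values and bone mineral density. By-visit counts cannot give the number of newly abnormal patients; that follows from the arithmetic and needs no assumption. How many patients would be affected is unknown, and every magnitude above is an assumed illustration.

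A reader might go further and doubt the primary safety results. The documents do not support that: the treatment-emergent adverse event tables are unaffected, and no test or error rate is involved. For the neurological examination the gap matters least, since most patients are likely to be abnormal at entry and neurological change is tabulated through ICARS change and CGI-C.

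One limit applies to any remedy. OLE-IEDAT baseline is the final ATTeST evaluation. For patients already on active drug in ATTeST, new means new since that baseline, not since first exposure.

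**What to change.** - **ECG (SAP 10.7.8 and index 12.1):** add a shift table of the investigator's interpretation (normal / abnormal not clinically significant / abnormal clinically significant) from OLE-IEDAT baseline to each 6-monthly visit. Use the format planned for special laboratory parameters and bone mineral density. Count one result per patient per visit, with patients having both a baseline and a visit result as the denominator. If the eCRF holds three ratings per evaluation, state how they become one and apply the rule consistently at baseline and follow-up.
- **Physical examination (SAP 10.7.7 and index 12.1):** add the same baseline-to-visit shift by body system, not as the worst category across systems, using the pre-infusion result at the 6-monthly visits.
- **Neurological examination:** a shift table is optional.
- **Worst post-baseline value:** add such a count only if it is read with the exposure table, because it rises with follow-up even without a trend.
- **Footnote:** say that new means since OLE-IEDAT baseline.

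If the sponsor prefers by-visit counts alone, one sentence in SAP 3.6 should say so.

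The cost is a little extra programming from data already collected, with a baseline already defined in SAP 7.1. The main drawback is sparse cells across the seven ATTeST group columns; a total column would be the readable one.

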#### **10.7.9 C-SSRS**

All recorded C-SSRS data are included in listings for the SAF.

The ideation summary score is summarized at each scheduled visit as a continuous variable, Additionally the ideation summary score is analysed as a categorical variable. Both analyses are performed separately for the Children's scale and the Adult's Scale as described in section 8.1 on the SAF.

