### **C-SSRS**

The Columbia Suicide Severity Rating Scale (C-SSRS) is a suicidal ideation rating scale which rates individual’s degree of suicidal ideation on a scale, ranging from "wish to be dead" to "active suicidal ideation with specific plan and intent." (Posner, et al., 2011). At each visit, patients are assigned an ideation severity score of 0 (no ideation present) to 5 (active suicidal ideation with plan and intent) based on their most severe suicidal ideation since the last visit as recorded in the eCRF. This is derived as 0 if the question “Wish to be dead” is marked as “No” and is derived as 1 to 5 based on the response to “Most severe ideation (Type#(1-5))”. If one of the two variables is missing for a visit, the ideation severity score is also regarded as missing.

Patients under the age of 12 years at the baseline visit would use the pediatric version of the scale throughout the study. Results are recorded on the ‘C-SSRS Children’s Since Last Visit’ or ‘C-SSRS Adult’s Since Last Visit’ eCRF page as appropriate.

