### Laboratory Values

|                  |   |     |   |
|------------------|---|-----|---|
| Table 14.3.2-1.1 | Summary of Hematology Laboratory Parameters         | SAF | U |
| Table 14.3.2-1.2 | Summary of Clinical Chemistry Laboratory Parameters | SAF | R |
| Table 14.3.2-1.3 | Summary of Special Laboratory Parameters            | SAF | R |
| Table 14.3.2-1.4 | Summary of Urinalysis Laboratory Parameters         | SAF | U |

|                     |  |     |   |
|---------------------|--|-----|---|
| Table 14.3.2-2.1    | Summary of Clinically Notable Hematology Laboratory Parameters         | SAF | U |
| Table 14.3.2-2.2    | Summary of Clinically Notable Clinical Chemistry Laboratory Parameters | SAF | R |
| Table 14.3.2-2.3    | Summary of Clinically Notable Urinalysis Laboratory Parameters         | SAF | R |
| Table 14.3.2-3.1    | Summary of Shift in Special Laboratory Parameters from Baseline        | SAF | U |
| Other Safety |  |     |   |
| Table 14.3.3-1.1    | Summary of Culture-Based Sterility Test                                | SAF | U |
| Table 14.3.-1.2     | Summary of Process Events  | SAF | U |
| Table 14.3.3-2.1    | Summary of Vital Sign Data   | SAF | U |
| Table 14.3.3-2.2    | Summary of Clinically Notable Change from Baseline Vital Signs         | SAF | U |
| Table 14.3.3-3.1    | Summary of Physical Examination Data                                   | SAF | U |
| Table 14.3.3-3.2    | Summary of Neurological Examination Data                               | SAF | R |
| Table 14.3.3-4      | Summary of ECG Data  | SAF | U |
| Table 14.3.3-5.1    | Summary of Columbia-Suicide Severity Rating Scale (C-SSRS) Children's  | SAF | U |
| Table 14.3.3-5.1    | Summary of Columbia-Suicide Severity Rating Scale (C-SSRS) Adult's     | SAF | R |
| Table 14.3.3-6.1    | Summary of Bone Mineral Density z-scores                               | SAF | U |
| Table 14.3.3-6.2    | Summary of Shift in Bone Mineral Density z-scores from Baseline        | SAF | U |
| Table 14.3.3-7.1    | Summary of Tanner Staging data   | SAF | U |

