### C-SSRS

|                     |   |     |   |
|---------------------|---|-----|---|
| Listing 16.2.10-4.1 | Listing of C-SSRS (Children's) Data – Ideation and Intensity  | SAF | U |
| Listing 16.2.10-4.2 | Listing of C-SSRS (Children's) Data – Behaviour and Lethality | SAF | U |
| Listing 16.2.10-4.3 | Listing of C-SSRS (Adults) Data – Ideation                    | SAF | U |
| Listing 16.2.10-4.4 | Listing of C-SSRS (Adults) Data – Intensity                   | SAF | U |
| Listing 16.2.10-4.5 | Listing of C-SSRS (Adults) Data – Behaviour and Lethality     | SAF | U |

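### The C-SSRS tables cover only the per-visit ideation score: suicidal behaviour is listed but not tabulated, and no count of patients ever affected is defined

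*SAP*

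**What the plan says.** Protocol section 13 names the C-SSRS among the evaluations on which safety and tolerability, the primary objective, will be judged. The schedule of visits places it at screening, at each of Months 1 to 12 and at the safety follow-up visit, with the yearly pattern repeated. Protocol 13.7 specifies the since-last-visit version.

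SAP 7.4.8 (C-SSRS) sets the unit of analysis: "At each visit, patients are assigned an ideation severity score of 0 (no ideation present) to 5". Two eCRF items feed the score, the wish-to-be-dead question and the most severe ideation type, coded 1 to 5. The zero rule reads "This is derived as 0 if the question “Wish to be dead” is marked as “No" and the missing-data rule reads "If one of the two variables is missing for a visit, the ideation severity score is also regarded as missing". No behaviour item enters the derivation.

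SAP 10.7.9 puts all C-SSRS data in listings and then describes the tables: "The ideation summary score is summarized at each scheduled visit as a continuous variable", and "Additionally the ideation summary score is analysed as a categorical variable". Both analyses are run separately for the Children's and Adult's scales. The table list in SAP 12.1 has two matching entries, "Summary of Columbia-Suicide Severity Rating Scale (C-SSRS) Children's" and its Adult's counterpart. In SAP 12.3, "Behaviour and Lethality" appears only in the titles of Listings 16.2.10-4.2 (children) and 16.2.10-4.5 (adults). SAP 7.1 sends data from unscheduled visits to listings.

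The protocol synopsis says "Descriptive statistical analyses of changes from baseline will be performed for all safety parameters", and SAP 8.3 commits to descriptive summaries of all safety data.

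**The concern.** The instrument records ideation on one side and behaviour and lethality on the other. The two tables carry the name of the whole scale but contain only ideation. Someone who reads the tables and not the listings would learn nothing about behaviour.

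The second gap is the unit of counting. Protocol 13.7 excludes subjects with suicidal ideation, so the natural safety question for a long extension is how many patients had any ideation or behaviour after baseline. A score that starts afresh at each visit, summarised visit by visit, does not answer that. Nor does any table combine the two scales, so no study-wide count exists. What is at stake is whether the report can state a basic patient-level result for a named safety measure without someone counting by hand from listings.

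**Working it through.** The plan states no figure on this point, so the check is a reading of the derivation, the table list and the listing list, followed by a short count.

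**1. What reaches a table.** SAP 12.1 has two C-SSRS tables. Under SAP 10.7.9 both hold the ideation score: 2 of 2 tables on ideation, 0 on behaviour, 0 with a patient-level count. SAP 12.3 has five C-SSRS listings (16.2.10-4.1 to 16.2.10-4.5), and two of these carry behaviour and lethality.

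**2. A patient with behaviour but no ideation.** Apply SAP 7.4.8 with the wish-to-be-dead item answered No:

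| Ideation type field | Zero rule applied first | Missing rule applied literally |
|---|---|---|
| blank | 0 | missing |
| 2 recorded | 0 | 0 |

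The type field is coded 1 to 5 and has no value for absence of ideation. If it had to be filled in, a patient without ideation would have no valid route to 0, so 0 is the workable reading. Under either reading the behaviour does not show. The second row is a side finding: a recorded ideation type is overridden by a No on the first item.

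**3. By-visit rows against patients ever affected.** The first year has 12 monthly post-baseline assessments plus the safety follow-up, 12 + 1 = 13 occasions. Suppose, for illustration, that six visits each show one patient with ideation above 0.
- Sum of the by-visit entries: 6 × 1 = 6.
- Fewest patients consistent with this: 1 (the same patient at all six visits).
- Most patients consistent with this: 6 (a different patient each time).

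The table looks the same in both cases. Only a patient-level derivation, such as the worst post-baseline score, separates them. The six is an assumption; the documents give no event frequency.

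**4. The categorical analysis.** The text attaches scheduled visits to the continuous summary only. Because the score is defined per visit and no post-baseline maximum is specified, the categorical analysis does not yield a patient-level count either. The table shells are not in the documents.

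**5. Practice elsewhere in the SAP.** SAP 10.7.6 counts patients who had one or more clinically notable vital-sign changes. SAP 10.7.1 counts patients with one or more TEAE, serious TEAE or AESI. SAP 10.7.9 has no equivalent.

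**The case against.** The case on the other side is that little is hidden. Every C-SSRS item is listed, the study is descriptive with no hypothesis tests, and the synopsis sentence on safety parameters is followed by one saying that abnormal values will be identified and listed, which is what happens to behaviour. All of that is true and limits the weight of the point. It does not supply the missing summary, and SAP 8.3 promises summaries of all safety data, not listings alone.

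A reader might infer three stronger things, which the documents do not support.

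- *That a rare ideation event would vanish into a near-zero visit mean.* It would not. The categorical analysis would show one patient in the relevant category, and the continuous summary under SAP 8.1 prints the maximum. A dilution calculated on 150 patients would also be misplaced: 150 is the maximum expected enrolment, while the tables are split by scale and show the seven ATTeST treatment groups.
- *That an attempt would appear in no table, or that the report would read as free of suicidality.* This goes beyond the C-SSRS tables. An attempt reported as an adverse event or SAE would be counted at patient level in the adverse event tables. The C-SSRS sections do not require behaviour to be recorded as an AE, so that route is likely but not guaranteed.
- *That depression on the AESI list makes suicidality a declared special interest.* In SAP 7.4.8 depression is listed as a sign of adrenal insufficiency, so it lends no support here.

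One practical objection also stands: counting unscheduled visits departs from SAP 7.1 and needs a new derivation, so the change is small but not entirely free.

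**Conclusion.** The point holds in a limited form. Neither C-SSRS table can show suicidal behaviour, and neither can show how many patients were ever affected by ideation or behaviour. A patient with behaviour and no ideation appears there as 0, or as missing under the literal missing-data rule. The size is structural, not numerical: one part of the instrument is left untabulated and one patient-level count is absent. How many patients this would affect cannot be estimated from the documents.

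The conclusion rests on the text of SAP 7.4.8, 10.7.9 and the output lists, and assumes that the table shells add nothing beyond them. It does not imply lost data, concealed ideation scores or a failure of adverse event reporting. It is a worthwhile, low-cost improvement to the reporting of a named measure under the primary safety objective.

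**What to change.** Add to the C-SSRS summaries n (%) of patients with:
- any post-baseline suicidal ideation, by worst category;
- any post-baseline suicidal behaviour;
- either of these.

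Present these by scale and pooled over both scales. Include unscheduled visits in the ever-affected counts, and state this as an exception to the SAP 7.1 rule. Keep the mean of the ordinal score as secondary only.

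While the section is open, reconcile the zero rule with the missing-data rule in SAP 7.4.8, and give the Children's and Adult's tables, both now numbered 14.3.3-5.1, distinct numbers.

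The cost is one small patient-level derivation and a few table rows. The fields are already collected and listed, so nothing changes for sites or patients.
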